8.1.7 Allergic Contact Dermatitis (Skin Sensitization) Assessment

Allergic contact dermatitis (ACD), as an AE, may manifest as moderate/severe pruritis and moderate/severe erythema with or without vesicles/bullae.

In the case of a suspected AE of ACD, the medical monitor should be contacted to discuss the case. If the medical monitor and the investigator agree that the AE is suggestive of ACD, the assigned treatment should be withheld, the AE documented, and treated, if required, by concomitant therapy that can include topical corticosteroids at the discretion of the investigator. Once the AE of ACD is resolved, in the opinion of the investigator, any concomitant therapy for this AE should be stopped, and the assigned treatment should be restarted (i.e., re-challenge exposure) after discussion with the medical monitor. If there is recurrence, an AE of ACD is confirmed and should be documented as an AE that is related to the assigned treatment.

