9.2 Adverse Events

9.2.1 Definitions of Adverse Events

According to 21 CFR Parts 312.32 and 320.32 (IND Safety Reporting, Applicability of Requirements Regarding an "Investigational New Drug Application"), Food and Drug Administration (FDA) Guidance for Industry (Investigational New Drug Safety Reporting Requirements for Human Drug and Biological Products and Safety Reporting Requirements for Bioavailability and Bioequivalence Studies in Humans) (Federal Register/Vol. 75, No. 188/September 29, 2010) and International Council on Harmonisation (ICH) E2A (Clinical Safety and Data Management: Definitions and Standards for Expedited Reporting):

An adverse event (AE) means any untoward medical occurrence associated with the use of a drug in humans, whether or not considered drug related.

A suspected adverse reaction (SAR) means any AE for which there is a reasonable possibility that the drug caused the AE.

The following information should be considered when determining whether or not to classify a test result, medical condition, or other incident as an AE:

Adverse events will be recorded from the time of informed consent.

Abnormal laboratory values should not generally be recorded as AEs unless an intervention is required, the laboratory abnormality results in an SAE, the lab abnormality results in study termination or interruption/discontinuation of study treatment, or the lab abnormality is associated with clinical signs or symptoms. When recording an AE resulting from a laboratory abnormality, the resulting medical condition rather than the abnormality itself should be recorded (e.g., record "anemia" rather than "low hemoglobin").

Complications that occur in association with a protocol-mandated intervention (e.g., invasive procedures such as biopsies) should be recorded as AEs.

Whenever possible, the Investigator should group signs or symptoms that constitute a single diagnosis under a single event term. For example, cough, rhinitis, and sneezing might be grouped together as "upper respiratory tract infection." If possible, abnormal laboratory results that meet the definition of an AE (see above) should be reported as a clinical diagnosis rather than the abnormal value itself (e.g., "anemia" rather than "decreased blood count").

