#### 9.2 Adverse Events

Treatment-emergent adverse events (TEAEs) are defined as those adverse events (AEs) with onset during or after the first dose of study drug or existing events that worsened after the first dose during the study. Treatment-emergent AEs will be summarized by treatment group and severity.

Partial or completely missing AE start dates will be imputed as follows:

- 1. If the year and month are known:
  - a. If the year and month are the same as the year and month of the treatment start date, impute to treatment start date.
  - b. Otherwise, use the 1st of the month.
- 2. If only the year is known:
  - a. If the year is the same as the year of treatment start date, impute to treatment start date.
  - b. Otherwise, impute to January 1st of that year.
- 3. If the date is completely missing, impute to treatment start date.

Partial or completely missing AE end dates will be imputed in the same manner, with end of treatment date or end of study replacing treatment start date in the algorithm.

AE listings will display the imputed dates.

Verbatim terms on case report forms will be mapped to preferred terms and system organ classes using the latest version of MedDRA.

At Visits 5, 6, 7, 8, 9, 12 (EOT), and 13 (Follow-up), treatment-emergent adverse events (TEAEs) in the Safety Population will be summarized by severity in the following tables: all reported TEAEs, all SAEs, all treatment-related SAEs, treatment-related TEAEs, severe TEAEs, TEAEs leading to dose interruption, TEAEs leading to study discontinuation, TEAEs of special interest, and anticholinergic TEAEs. Additionally, local site reaction TEAEs will be summarized in the Safety Population by severity at Visits 5, 6, 7, 8, 9, 12 (EOT), and Visit 13 (Follow-up). Local site reaction TEAEs are defined as AEs coded to the system organ class of general disorders and administration site conditions and, at a minimum, the following preferred terms:

- Application site pruritus
- Application site pain
- Application site irritation
- Application site dermatitis
- Application site rash
- Application site erythema
- Application site discolouration
- Application site dryness
- Application site exfoliation
- Application site reaction
- Application site warmth

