Each of the above tables will be produced for cumulative TEAEs up to the current visit reported by all Safety Population subjects (including those absent from the current visit). At each of the visits, each of the above tables will summarize the subject incidence (frequency count and %) for the specified TEAE, mapped to MedDRA System Organ Class and Preferred Term, according to the highest severity reported. Subjects with only unknown severity for a TEAE will be counted under the severity unknown category.

Summaries that are displayed by system organ class and preferred terms will be ordered by descending incidence of system organ class in the total column and preferred term within each system organ class. The total column will not be displayed and will only be used for sorting. TEAEs of special interest include the following:

- Vision blurred
- Mydriasis (unilateral or bilateral)
- Urinary hesitation

An overall TEAE summary table by treatment group with the total number of TEAEs and the number and percentage of subjects with at least one of the following will be presented: TEAE, serious TEAE, treatment-related TEAE, treatment-related serious TEAE, severe TEAE, TEAE leading to dose interruption, TEAE leading to study discontinuation, TEAEs of special interest, anticholinergic TEAEs, anticholinergic TEAEs leading to study discontinuation, local site reaction TEAEs, local site reaction TEAEs leading to study discontinuation. The overall summary table will also display the number and percent of subject deaths, should any deaths occur.

The number of subjects with study discontinuations due to TEAEs, the number of subjects with study discontinuations due to anticholinergic TEAEs, and the number of subjects with study discontinuations due to AESIs will be plotted as a bar chart versus time on treatment. Time on treatment is defined as the earlier of treatment end date or study discontinuation date – treatment start date + 1. Time on treatment will be displayed in categories of 0 to 2 weeks, >2 to 4 weeks, >4 to 6 weeks. Weeks are defined as 7 days. The follow-up visit is excluded.

The number of treatment-related TEAEs and the number of local site reaction TEAEs will be plotted versus time on treatment. The number of subjects with a treatment-related TEAE and the number of subjects with a local site reaction TEAE will be plotted versus time. Time for these plots will be displayed as weeks 1-8 which includes the follow-up visit.

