# 9.2.1 Allergic Contact Dermatitis

Allergic contact dermatitis (ACD), as an AE, may manifest as moderate to severe pruritus and moderate to severe erythema with or without vesicles or bullae.

In the case of a suspected AE of ACD, the Medical Monitor should be contacted to discuss the case and the following steps should be taken at the discretion of the Investigator: 1) assigned treatment should be withheld, 2) the AE of ACD documented, 3) any necessary concomitant treatment should be administered, which can include topical corticosteroids.

Once the AE of ACD is resolved in the opinion of the Investigator, any concomitant therapy for this AE should be stopped, and the assigned treatment should be restarted after discussion with the Medical Monitor (i.e., re-challenge exposure). If there is a recurrence, ACD is confirmed and should be documented as an AE that is related to the assigned study treatment.

Confirmed ACD cases are defined as cases which led to recurrence of ACD event following treatment restart. Suspected ACD cases are those events with "Suspected Allergic Contact Dermatitis" checked on the AE eCRF page. The following parameters will be summarized with descriptive statistics by treatment group to characterize instances of ACD:

- Number and percentage of subjects with treatment-emergent ACD events by severity
- Number and percentage of subjects with treatment-emergent ACD events leading to treatment discontinuation by severity

- Number and percentage of subjects who restarted treatment after the ACD event and later discontinued treatment. These will be confirmed ACD events.
- Time to first confirmed ACD event in days defined as: start date of the ACD event treatment start date + 1.
- Time to first treatment interruption due to confirmed ACD event in days defined as: last exposure date prior to ACD event leading to interruption treatment start date + 1.
- Duration of treatment interruption in days defined as: date of first exposure after end of ACD event - date of last exposure prior to ACD event leading to interruption + 1. If the ACD event is ongoing, either the treatment discontinuation date or first available exposure date after the start of the event will be used to calculate duration. If subject experienced more than one interruption due to ACD, durations of interruptions will be summed.
- Time to treatment discontinuation in days defined as: date of treatment discontinuation date of treatment start + 1.

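### Local site reaction TEAEs are selected by MedDRA class rather than by site, so an axillary reaction coded to another class would be missing from those outputs

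*SAP*

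**What the plan says.** SAP 9.2 sets two conditions for a local site reaction TEAE. The first is the class: "Local site reaction TEAEs are defined as AEs coded to the system organ class of general disorders and administration site conditions". The second is the preferred term, joined to the first by the words "conditions and, at a minimum, the following preferred terms". Eleven terms follow, all beginning Application site, and Application site dermatitis is one of them.

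The class is assigned by coding alone: "Verbatim terms on case report forms will be mapped to preferred terms and system organ classes using the latest version of MedDRA".

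The protocol shapes what is coded. Its section 9.2.1 says: "Whenever possible, the Investigator should group signs or symptoms that constitute a single diagnosis under a single event term". Its section 8.1.7 treats ACD as an AE that "may manifest as moderate/severe pruritis and moderate/severe erythema with or without vesicles/bullae".

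The category feeds two entries in the overall TEAE summary ("local site reaction TEAEs, local site reaction TEAEs leading to study discontinuation"), a cumulative table at each of seven visits, and two figures. SAP 13 records that the definition was added in the SAP, so the protocol has no competing version.

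**The concern.** The category is meant to describe what happens where the gel is applied, yet membership depends on the coded class. An investigator who groups axillary itch and redness into one diagnosis is following the protocol. If the verbatim term does not say that the event was at the application site, the coder may place it in another class. It then leaves the local-reaction outputs, although a single sign at the same site, coded to a listed term, would stay in. Two clinically identical reactions could be treated differently because two sites worded them differently.

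Local tolerability is part of the first study objective. What is at stake is whether the reported incidence of local reactions, and the count of those leading to study discontinuation, depends on wording.

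**Working it through.** The plan gives no figure to reproduce here. The check is to read the definition, trace its uses, and look for any text that restores events from other classes.

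1. **Reach of the definition.** The class and term conditions are joined by *and*. The phrase *at a minimum* attaches to the list of preferred terms. It allows more terms but does not touch the class. An event outside the class therefore fails, whatever terms are added.

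2. **What decides the class.** SAP 9.2 maps verbatim terms through MedDRA. Protocol 9.2.1.2 lists what is documented for each AE: dates, intensity, seriousness, relationship, action taken and outcome. Anatomical site is not among them. On the documents as they stand, the verbatim wording is what carries the site.

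3. **Two recordings of one reaction.**

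| How the axillary reaction is coded | Local site reaction outputs | General TEAE tables |
|---|---|---|
| To a listed term, e.g. Application site dermatitis | Counted | Counted |
| As a diagnosis in another class | Not counted | Counted |

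4. **Outputs that use the definition** (SAP 9.2, 15 and 16).
   - Cumulative tables 14.3.1.2.10 to 14.3.1.8.10, one for each of Visits 5, 6, 7, 8, 9, 12 and 13: 7 tables.
   - Table 14.3.1.1: 2 rows.
   - Figures 14.3.1.1.6 (events) and 14.3.1.1.7 (subjects): 2 figures.

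5. **Text that would restore the event.** None was found. SAP 9.2.1 summarises ACD separately, in Table 14.3.1.9 and Listing 16.2.7.5, but no rule says whether an ACD case also counts as a local site reaction. The two displays cannot simply be added: a case coded to an application-site term appears in both, and one coded elsewhere appears only in the ACD display. The discontinuation counts differ too, because the ACD summary counts stopping treatment and the local-reaction row counts leaving the study.

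6. **Closing the list.** SAP 4 and 5.2 fix the analysis populations and the major violations before unblinding. SAP 9.2 has no such rule for the open-ended term list.

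7. **Scale.** The documents give no count of affected events. With the planned 175 subjects per arm (Protocol 2), one subject missed for this reason changes that arm's incidence by 1/175 = 0.0057, or about 0.6 percentage points. This holds only if the subject has no other counted local reaction, because the tables count subjects.

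**The case against.** The best reply is that the plan already covers most of this. Application site dermatitis, rash, erythema, pruritus and irritation are all listed, so a dermatitis at the site has a natural home. ACD is summarised in detail by severity, treatment discontinuation and timing. An event coded to another class still appears in the all-TEAE tables and, where it qualifies, in the treatment-related, severe, dose-interruption and study-discontinuation tables. Safety analysis is descriptive, and no endpoint or error rate is involved. All of this stands, and it is why the point is minor. It does not give other axillary skin diagnoses a dedicated display, and it does not say how the ACD and local-reaction displays overlap.

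A reader might infer more than the documents support:

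- **That ACD necessarily drops out.** The documents do not say which term or class a contact dermatitis would receive. They support only that an event coded outside the class drops out.
- **That every local-reaction display is affected.** The visit-scored local tolerability outputs (SAP 9.3; Tables 14.3.6.1 to 14.3.6.3, Figure 14.3.1.2) do not depend on MedDRA coding.
- **That the omitted events are the ones that lead to stopping and differ by arm.** No passage shows this. Protocol 8.1.7 describes withholding and then restarting treatment, and Protocol 1 describes earlier local reactions as mostly minimal and transient.
- **That the understatement can be stated in percentage points.** This needs an event count, which the documents do not give.

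**Conclusion.** The point holds as a gap in the definition. SAP 9.2 filters on class, and an axillary reaction coded to another class would be missing from the seven tables, two summary rows and two figures, although the same reaction coded to a listed term would be included. The conclusion rests on the wording of SAP 9.2 and on the absence of any text that restores such events. Whether any event is affected depends on verbatim wording and coding practice, so the size is unknown and could be zero. Nothing is lost from safety reporting as a whole. This is a minor improvement worth making because it is cheap.

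**What to change.** In SAP 9.2, define a local site reaction TEAE by site and not by class, as any TEAE that meets at least one of these conditions:

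- it has one of the listed preferred terms;
- the suspected ACD box is ticked on its AE form;
- it has a term in any class and a verbatim that places it at the axilla or application site.

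Settle the term list by blinded review before unblinding, and count each subject once. Keep Table 14.3.1.9 as a separate display, and add a footnote giving its overlap with the local-reaction category.

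The change uses data that the SAP already expects on the AE form and alters no clinical procedure. It costs a wording change and a short blinded term review. The second condition brings in every ticked case, confirmed or not, and repeats cases shown in Table 14.3.1.9, which is why the footnote is needed. Reported local-reaction rates may rise slightly.

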# 9.2.1 Allergic Contact Dermatitis

Allergic contact dermatitis (ACD), as an AE, may manifest as moderate to severe pruritus and moderate to severe erythema with or without vesicles or bullae.

In the case of a suspected AE of ACD, the Medical Monitor should be contacted to discuss the case and the following steps should be taken at the discretion of the Investigator: 1) assigned treatment should be withheld, 2) the AE of ACD documented, 3) any necessary concomitant treatment should be administered, which can include topical corticosteroids.

Once the AE of ACD is resolved in the opinion of the Investigator, any concomitant therapy for this AE should be stopped, and the assigned treatment should be restarted after discussion with the Medical Monitor (i.e., re-challenge exposure). If there is a recurrence, ACD is confirmed and should be documented as an AE that is related to the assigned study treatment.

Confirmed ACD cases are defined as cases which led to recurrence of ACD event following treatment restart. Suspected ACD cases are those events with "Suspected Allergic Contact Dermatitis" checked on the AE eCRF page. The following parameters will be summarized with descriptive statistics by treatment group to characterize instances of ACD:

- Number and percentage of subjects with treatment-emergent ACD events by severity
- Number and percentage of subjects with treatment-emergent ACD events leading to treatment discontinuation by severity

- Number and percentage of subjects who restarted treatment after the ACD event and later discontinued treatment. These will be confirmed ACD events.
- Time to first confirmed ACD event in days defined as: start date of the ACD event treatment start date + 1.
- Time to first treatment interruption due to confirmed ACD event in days defined as: last exposure date prior to ACD event leading to interruption treatment start date + 1.
- Duration of treatment interruption in days defined as: date of first exposure after end of ACD event - date of last exposure prior to ACD event leading to interruption + 1. If the ACD event is ongoing, either the treatment discontinuation date or first available exposure date after the start of the event will be used to calculate duration. If subject experienced more than one interruption due to ACD, durations of interruptions will be summed.
- Time to treatment discontinuation in days defined as: date of treatment discontinuation date of treatment start + 1.
- Time from treatment restart to treatment discontinuation due to recurrence ACD event in days defined as: date of treatment discontinuation date of first exposure after end of ACD event + 1.

Percentages will be out of the Safety Population in each group. A by-subject listing will also be presented.

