Approximately 350 subjects, at up to approximately 45 clinical sites in the United States, will be randomized to receive either sofpironium bromide gel, 15% or vehicle gel (placebo) in a balanced 1:1 ratio in order to obtain approximately 300 evaluable subjects at the end of study.

Subjects will apply the investigational product (either sofpironium bromide gel, 15% or vehicle gel) once daily at bedtime to each axilla for 42 consecutive days.

Gravimetric measurements of sweat production and patient-reported outcomes HDSM-Ax-7 and Dermatology Life Quality Index (DLQI) (via electronic clinical outcomes assessment [eCOA] technology) will be recorded during the study at predefined time points. Patient Global Impression of Severity (PGI-S) will be administered

with each administration of the HDSM-Ax, and the Patient Global Impression of Change (PGI-C) will be administered at the Day 43 visit (End of Treatment) only. Vital signs, local tolerability assessments, and adverse events will be collected at each visit. Blood and urine samples will be collected and analyzed at the Screening Visit and at the End of Treatment Visit for routine hematology, chemistry, and urinalysis parameters. Urine pregnancy testing for FOCBP will be performed at the Screening Visit, Baseline Visit, Visit 8 and End of Treatment.

A total of 13 scheduled visits will take place over approximately 11 to 15 weeks, depending on when the Baseline Visit (treatment) is scheduled after the three (3) screening period visits: initial screening, GSP1, and GSP2.

Test Product, Dose, and Mode of Administration

Either sofpironium bromide gel, 15%; or vehicle gel (placebo) topically applied to the axillae

Duration of Treatment

Forty-two days followed by a 14-day post-treatment follow-up visit

Safety Assessments

- Physical examination
- Vital signs
- Clinical laboratory assessments
- Urinalysis
- Collection of adverse events
- Subject-reported local tolerability assessments
- Investigator-reported local tolerability assessments

Efficacy Assessments

The following assessment measures will be conducted to evaluate the efficacy of sofpironium bromide gel:

- Hyperhidrosis Disease Severity Measurement-Axillary (HDSM-Ax-7) as measured by the subject (for subjects ≥12 years of age)
- Hyperhidrosis Disease Severity Measurement-Axillary, Child (HDSM-Ax-7, Child) as measured by the subject (for subjects ≥9 to <12 years of age)
- Gravimetrically measured sweat production (GSP)

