2 STUDY DESIGN

This is a multicenter, randomized, double-blinded, vehicle-controlled, Phase 3 study to evaluate the safety and efficacy of topically applied sofpironium bromide gel, 15% in subjects with primary axillary hyperhidrosis.

Approximately 350 subjects, at up to approximately 45 clinical sites in the US, will be enrolled to obtain approximately 300 evaluable subjects at the end of study.

Subjects will be randomized 1:1 to receive sofpironium bromide gel, 15% or vehicle gel (175 subjects dosed with 15% gel and 175 subjects dosed with vehicle gel). Subjects will apply the investigational product once daily at bedtime to their axillae for 42 consecutive days.

Patient-reported outcomes HDSM-Ax, Patient Global Impression of Severity (PGI-S), Patient Global Impression of Change (PGI-C; EOT only), and DLQI, as well as Investigator-reported GSP, will be recorded during the study at predefined time points. Vital signs and local tolerability assessments will be collected at Visits 4 through 9 and Visits 12 (EOT) and 13. Adverse events will be collected at each post-Screening visit. Blood and urine samples will be collected and analyzed at Screening and Visit 12/EOT for routine hematology, chemistry, and urinalysis parameters. Additionally, a urine pregnancy test (UPT) for females of child-bearing potential (FOCBP) will be collected and analyzed at Visits 1, 4, 8, and 12.

A total of 13 scheduled visits will take place over approximately 11 to 15 weeks, depending on when the Baseline Visit (treatment) is scheduled after the three (3) screening period visits: initial screening, GSP1, and GSP2. See Section 7.1 for an events table of this study.

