7.4 Early Discontinuation of Subjects

It is the right and duty of the Investigator to discontinue a subject's participation if the subject's health or wellbeing is threatened by continuation in the study. In the event of premature discontinuation, the Investigator should determine the primary reason for discontinuation. A subject may be discontinued from the study if any of the following circumstances occur:

- The subject experiences a SAE rendering him or her unable to continue study participation.
- The subject experiences an AE that in the opinion of the Investigator may pose a significant risk for continued participation of the subject in the study.
- The subject is unable to physically or mentally tolerate the use of the investigational product.
- An exclusion criterion becomes apparent at any time during the study; the Medical Monitor must be contacted to discuss prior to discontinuing subject participation.
- The subject is not compliant with the study procedures; the Medical Monitor must be contacted to discuss prior to discontinuing subject participation.
- The subject voluntarily withdraws from the study. When possible, attempt to identify the reason the subject withdrew consent and document with particular attention paid to whether an underlying AE is at cause.
- The subject becomes pregnant.
- If for any reason per the Investigator's or the Sponsor's judgment, discontinuation is in the subject's best interest.

Subjects who discontinue the study prior to the completion of all treatment visits will be asked to complete the evaluations corresponding to Visit 12 (Day 43, End of Treatment). The Sponsor will be notified of early discontinuation as soon as possible during the study.

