#### Safety Population

The Safety Population will include all subjects randomized in the study who received study drug, either vehicle or sofpironium bromide, 15%, at least once. Subjects will be analyzed according to the treatment actually received. If a subject receives any sofpironium bromide gel, 15%, the subject will be analyzed in the sofpironium bromide gel group. Otherwise the subject will be included in the vehicle group.

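### SAP 9.2.1 defines confirmed ACD by recurrence after restart but counts it by restart and later discontinuation, and under neither rule can a reader see who was never re-challenged

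*SAP*

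**What the plan says.** SAP 9.2.1 gives the rule in words: "Confirmed ACD cases are defined as cases which led to recurrence of ACD event following treatment restart". Protocol 8.1.7 applies the same test: "If there is recurrence, an AE of ACD is confirmed and should be documented as an AE that is related to the assigned treatment".

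SAP 9.2.1 then lists eight items to summarise by treatment group. The third is the only one that counts confirmed cases as such: "Number and percentage of subjects who restarted treatment after the ACD event and later discontinued treatment. These will be confirmed ACD events". The fourth and fifth, time to the first confirmed event and time to the first interruption due to a confirmed event, are restricted to confirmed cases.

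On the denominator the section says: "Percentages will be out of the Safety Population in each group". SAP Section 4 defines that set: "The Safety Population will include all subjects randomized in the study who received study drug" at least once. Treatment is applied "once daily at bedtime to each axilla for 42 consecutive days" (Protocol synopsis, Study Design), and neither document describes an extension of dosing after an interruption.

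The first two items need no re-challenge. They are all treatment-emergent ACD events, and those that led to stopping treatment, each by severity. A by-subject listing is also planned (Listing 16.2.7.5). The summary is Table 14.3.1.9.

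**The concern.** The section has two rules for the same label. The definition requires a recurrence. The counting row requires a restart and a later stop, whatever the reason for stopping. A programmer can follow either, and the two can give different numbers. Under SAP 3.1 continuous summaries show the number of subjects, so the time summaries could even report a different count of confirmed cases from the counting row in the same table.

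Both rules also require a restart within a fixed dosing period. Subjects with a late onset, and subjects who stop without restarting, are never tested. The plan has no row for them and none for subjects re-challenged without recurrence. A reader who sees few confirmed cases cannot tell whether re-challenge was mostly negative or mostly did not happen.

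**Working it through.** The plan states no ACD rate or duration, so there is no figure of its own to reproduce. The check compares the two rules and then shows what they imply under stated assumptions.

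**1. The two rules side by side**, for a subject with a first ACD episode:

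| Course | Definition | Counting row |
|---|---|---|
| Restarts, recurs, stops | confirmed | counted |
| Restarts, recurs, completes | confirmed | not counted |
| Restarts, no recurrence, stops for another reason | not confirmed | counted |
| Restarts, no recurrence, completes | not confirmed | not counted |
| Never restarts | not confirmed | not counted |

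The rules disagree in the second and third courses. Neither separates the fourth from the fifth.

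**2. Direction of error in the counting row.** Assume 10 suspected cases of which 5 are true, 80% restarted, and recurrence in every re-challenged true case and in no other.
- True cases restarted: 5 × 0.80 = 4.0. Other suspected cases restarted: 5 × 0.80 = 4.0.
- The definition gives 4.0 confirmed against 5 true.
- If 60% of recurrent subjects stop and no others do, the row gives 4.0 × 0.60 = 2.4.
- If all recurrent subjects stop and 30% of the others do, the row gives 4.0 + 4.0 × 0.30 = 5.2.

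The row can fall below or above the truth.

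**3. The definition as a lower bound.** The captured share of true cases is (share re-challenged) × (probability of recurrence). With assumed ranges of 25–75% and 80–100%, it runs from 0.25 × 0.80 = 20% to 0.75 × 1.00 = 75%. For illustration, take the planned arms ("175 subjects dosed with 15% gel and 175 subjects dosed with vehicle gel") and assume 10 true cases in an arm, which is 10/175 = 5.7%. If every re-challenge is positive, re-challenging 25%, 50% or 75% gives:
- 2.5/175 = 1.4%
- 5/175 = 2.9%
- 7.5/175 = 4.3%

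Confirmed over re-challenged would be 100% in all three. That is a recurrence proportion, and it does not estimate incidence.

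**4. The 42-day window.** Let r be days to resolution and s days from restart to recurrence, both assumed. With onset spread evenly over the dosing days, the last confirmable onset day is 42 − r − s, and the unconfirmable share is (r + s)/42.

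| r + s | Last confirmable onset | Unconfirmable |
|---|---|---|
| 3 + 1 | Day 38 | 4/42 = 10% |
| 7 + 3 | Day 32 | 10/42 = 24% |
| 14 + 3 | Day 25 | 17/42 = 40% |
| 14 + 7 | Day 21 | 21/42 = 50% |
| 21 + 7 | Day 14 | 28/42 = 67% |

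If only the restart must fall within dosing and a recurrence may be recorded later, the share is r/42: 7/42 = 17%, 14/42 = 33%, 21/42 = 50%.

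**5. Tilt of the time summaries.** Under 14 + 3, only onsets on Days 1 to 25 can enter. With even onset, and taking the event start as that of the first episode, the mean onset day among them is (1 + 25)/2 = 13. For all onsets it is (1 + 42)/2 = 21.5.

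**The case against.** The strongest reply is that nothing is hidden. All treatment-emergent ACD events, and those that end treatment, are tabulated without any re-challenge and on the same denominator. A low confirmed count therefore cannot conceal a high total. The listing shows each subject's course, the duration of interruption and time to treatment discontinuation are not limited to confirmed cases, and safety analyses carry no formal testing (SAP 9.1). All of this stands. A reader might infer that reactions severe enough to end treatment are left out of the ACD summary, or that the confirmed rate is the trial's measure of skin sensitisation. The documents support neither.

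A reader might also infer that the Safety Population is the wrong denominator. It is the usual one for incidence. Any shortfall lies in the numerator, in cases that were never tested.

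The third item could be read together with the definition, so that only recurrent subjects who then stop are counted. That is a fair reading, but the row would still miss recurrent subjects who complete treatment while labelling its count as confirmed.

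The route by which subjects stop without restarting is only general. Protocol 7.4 allows discontinuation when "The subject is unable to physically or mentally tolerate the use of the investigational product" but does not name ACD, while Protocol 8.1.7 expects a restart once the event resolves. How many would not restart is unknown. Adverse events are also collected through the follow-up visit on Day 57, so a recurrence need not be recorded by Day 42. This lowers the shares in step 4 as shown, if recurrence does not need several further doses.

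**Conclusion.** The point holds as a defect in definition and reporting. SAP 9.2.1 defines confirmed ACD one way and counts it another, and no planned row shows who was re-challenged. Under the definition the confirmed percentage is a lower bound on true ACD, provided that a recurrence is taken as true ACD. Under the counting row the error has no fixed direction, so it cannot be said that the confirmed rate must be understated. The two summaries restricted to confirmed events lean towards early onsets under either rule.

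The size of any shortfall cannot be derived from the documents. The 10% to 67% range rests on assumed durations, even onset, and recurrence needed by Day 42. The capture range of 20% to 75% rests on assumed re-challenge and recurrence proportions. Overall ACD incidence and the co-primary analyses are not affected.

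**What to change.** In SAP 9.2.1, state one definition of confirmed ACD and make the counting row follow it.

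In Table 14.3.1.9, split subjects with treatment-emergent ACD events by arm into three rows: re-challenged with recurrence (confirmed), re-challenged without recurrence, and not re-challenged. Give the reason for the last group (dosing period ended, treatment stopped, or event unresolved). Keep the Safety Population as denominator, footnote the confirmed percentage as a lower bound, and show recurrence among re-challenged subjects only as a supplementary proportion. Present the two time summaries for all treatment-emergent ACD events, with the confirmed subset shown separately.

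The cost is SAP wording and a few table rows, built from the adverse event and exposure dates that the section already uses. The presentation may look less favourable. The clinical re-challenge procedure is not changed.
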